9.2.1. Serious Adverse Events

An SAE is any AE from this study that results in one of the following:

- death
- initial or prolonged inpatient hospitalization
- a life-threatening experience (that is, immediate risk of dying)
- persistent or significant disability/incapacity
- congenital anomaly/birth defect
- important medical events that may not be immediately life-threatening or result in death or hospitalization but may jeopardize the patient or may require intervention to prevent one of the other outcomes listed in the definition above

Study site personnel must alert the Lilly clinical pharmacologist, CRP, CRS, or its designee of any SAE as soon as practically possible.

Additionally, study site personnel must alert Lilly Global Patient Safety or its designee of any SAE within 24 hours of investigator awareness of the event via a sponsor-approved method. If alerts are issued via telephone, they are to be immediately followed up with official notification on study-specific SAE forms. This 24-hour notification requirement refers to the initial SAE information and all follow-up SAE information.

Although all AEs are recorded in the eCRF after signing informed consent, SAE reporting to the sponsor begins after the patient has signed informed consent and has received IMP. However, if an SAE occurs after signing informed consent, but before receiving IMP, AND is considered reasonably possibly related to a study procedure then it MUST be reported.

Investigators are not obligated to actively seek AEs or SAEs in patients once they have discontinued from and/or completed the study (the patient's summary eCRF has been completed). However, if the investigator learns of any SAE, including a death, at any time after a patient has been discharged from the study, and the investigator considers the event reasonably possibly related to the study treatment or study participation, he or she must promptly notify Lilly.

Pregnancy (maternal or paternal exposure to IMP) does not meet the definition of an AE. However, to fulfill regulatory requirements, any pregnancy should be reported following the SAE process to collect data on the outcome for both mother and fetus.

9.2.1.1. Suspected Unexpected Serious Adverse Reactions

Suspected unexpected serious adverse reactions (SUSARs) are serious events that are not listed in the IB and that the investigator reports as related to IMP or procedure. Lilly has procedures

that will be followed for the recording and expedited reporting of SUSARs that are consistent with global regulations and the associated detailed guidances.

9.2.2. Complaint Handling

Lilly collects product complaints on IMPs and drug delivery systems used in clinical trials in order to ensure the safety of study participants, monitor quality, and to facilitate process and product improvements.

Patients should be instructed to contact the investigator as soon as possible if he or she has a complaint or problem with the IMP so that the situation can be assessed.

9.3. Treatment of Overdose

For the purposes of this study, an overdose of LY3298176 is considered any dose higher than the dose assigned through randomization.

Refer to the IB for LY3298176.

9.4. Safety

9.4.1. Laboratory Tests

For each patient, clinical laboratory tests detailed in [Appendix 2](#) should be conducted according to the Schedule of Activities (Section 2).

9.4.2. Vital Signs

For each patient, vital signs measurements should be conducted according to the Schedule of Activities (Section 2).

Blood pressure (BP) and pulse rate (PR) should be measured after approximately 5 minutes in the supine position.

If orthostatic measurements are required, patients should be supine for approximately 5 minutes and stand for at least 2 minutes. If the patient feels unable to stand, supine vital signs only will be recorded.

Unscheduled orthostatic vital signs should be assessed, if possible, during any AE of dizziness or posture-induced symptoms. Additional vital signs may be measured during each study period if warranted.

Body temperature will be measured as specified in the Schedule of Activities and as clinically indicated (Section 2).

9.4.2.1. Body Weight

Weight will be measured in a consistent manner using a calibrated scale according to the Schedule of Activities (Section 2). Patients will be weighed in light clothing at approximately the same time in the morning before dosing and after an overnight fast and evacuation of bowel and the bladder, if possible. During the treatment period, weight will be measured twice on each

scheduled occasion, with the patient stepping off the scale between measurements. Both weight measurements will be recorded in the source document and the eCRF. Wherever possible, the same scale will be used for all weight measurements throughout the study.

9.4.3. *Electrocardiograms*

For each patient, 12-lead digital ECGs should be collected according to the Schedule of Activities (Section 2).

Any clinically significant findings from ECGs that result in a diagnosis and that occur after the patient receives the first dose of the IMP should be reported to Lilly or its designee as an AE via eCRF.

For each patient, a single 12-lead ECG will be collected locally at screening and follow-up or early termination visit according to the Schedule of Activities (Section 2). At all other time points, ECGs will be collected and stored using an ECG machine provided by the central ECG vendor. The Day 1 predose ECG will be taken in triplicate every 15 minutes for 1 hour to establish a baseline. At all other scheduled times, consecutive triplicate ECGs will be obtained at approximately 1-minute intervals. Electrocardiograms may be obtained at additional times when deemed clinically necessary. Collection of more ECGs (more replicates) than expected at a particular time point is allowed to ensure high-quality records. All ECGs recorded should be stored at the investigational site.

Electrocardiograms must be recorded before collecting any blood for safety or PK tests. Patients must be supine for approximately 5 to 10 minutes before ECG collection and remain supine but awake during ECG collection.

Electrocardiograms will be interpreted by a qualified physician (the investigator or qualified designee) at the site as soon as possible after the time of ECG collection and ideally while the patient is still present to determine whether the patient meets entry criteria at the relevant visit(s) and for immediate patient management should any clinically relevant findings be identified.

If a clinically significant quantitative or qualitative change from baseline is identified (including, but not limited to, changes in QT interval/QT interval corrected for heart rate [QTc] using Fridericia's formula [QTcF] from baseline) after enrollment, the investigator will assess the patient for symptoms (for example, palpitations, near syncope, syncope) to determine whether the patient can continue in the study. The investigator or qualified designee is responsible for determining if any change in patient management is needed and must document his or her review of the ECG printed at the time of evaluation from at least one of the replicate ECGs from each time point. Any new clinically relevant finding should be reported as an AE.

Digital ECGs will be electronically transmitted to a central ECG laboratory designated by Lilly. The central ECG laboratory will perform a basic quality control check (for example, demographics and study details) and then store the ECGs in a database. At a future time, the stored ECG data may be overread at the central ECG laboratory for further evaluation of machine-read measurements or to meet regulatory requirements.

The machine-read ECG intervals and heart rate may be used for data analysis and report-writing purposes unless a cardiologist overread of the ECGs is conducted before completion of the final study report (in which case, the overread data would be used).

9.4.4. Safety Monitoring

The Lilly clinical pharmacologist, CRP, or CRS will monitor safety data throughout the course of the study.

Lilly will review SAEs within time frames mandated by company procedures. The Lilly clinical pharmacologist, CRP, or CRS will periodically review the following data:

- trends in safety data
- laboratory analytes
- serious and nonserious AEs, including AEs of special interest (for example, GI events, hypoglycemia, injection-site reactions, and hypersensitivity reactions) and reported and adjudicated pancreatitis

When appropriate, the Lilly clinical pharmacologist, CRP, or CRS will consult with the functionally independent Global Patient Safety therapeutic area physician or clinical research scientist.

In the event that safety monitoring uncovers an issue that needs to be addressed by unblinding at the group level, additional analyses of the safety data will be conducted by the personnel included in the Blinding/Unblinding Plan ([Appendix 8](#)).

9.4.4.1. Hepatic Safety

If a study patient experiences elevated ALT $\geq 3 \times$ ULN, ALP $\geq 2 \times$ ULN, or elevated TBL $\geq 2 \times$ ULN, liver tests ([Appendix 5](#)) should be repeated within 3 to 5 days including ALT, AST, ALP, TBL, direct bilirubin, γ -glutamyl transferase, and creatinine kinase to confirm the abnormality and to determine if it is increasing or decreasing. If the abnormality persists or worsens, clinical and laboratory monitoring should be initiated by the investigator on the basis of consultation with the Lilly clinical pharmacologist, CRP, or CRS. Monitoring should continue until levels normalize and/or are returning to approximate baseline levels.

Additional safety data should be collected if 1 or more of the following conditions occur:

- elevation of serum ALT to $\geq 5 \times$ ULN on 2 or more consecutive blood tests
- elevated serum TBL to $\geq 2 \times$ ULN (except for cases of known Gilbert's syndrome)
- elevation of serum ALP to $\geq 2 \times$ ULN on 2 or more consecutive blood tests
- patient discontinued from treatment because of a hepatic event or abnormality of liver tests
- hepatic event considered to be an SAE

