Informed consent	X						
Distribution of glucose meters, test strips, and diaries/SMPG training	X ^e	X					
7-point SMPG		X ^f					
Medical history	X						
Physical examination	X						
Medical assessment	X			X	X	X	
AEs/concomitant medications	X			X	X	X	X
Chest x-ray ^g	X						
Height and weight	X						
Body temperature	X						
Vital signs (BP/PR) ^{h,i}	X			X	X	X	
12-Lead ECG ^{i,j}	X			X	X	X	
PK sampling ^{k,l}				X	X	X	X
Clinical safety lab (hematology, chemistry, urinalysis) ^{m,n}	X			X	X	X	
Clinical safety lab (serology) ⁿ	X						
Pregnancy test (serum, urine) ^{n,o,p}	X						
Follicle-stimulating hormone ^{n,o}	X						
Urine drug and alcohol screen ^{n,p}	X						
Hemoglobin A1c ^{l,m}	X						
Fasting glucose, insulin, glucagon ^{l,m}				X	X	X	
Immunogenicity ^l					X	X	X

Study Schedule Protocol I8F-JE-GPGC Cohort 1 for Treatment Period

Procedure	Treatment Period (Cohort 1)																					
	-1	1	2	3	4	8	15	16	17	18	22 ±1	29	30	31	32	36 ±1	43 ±1	50	51	52	57	ET1 ^d
Inpatient stay at CRU ^q	X	X	X	X	X		X	X	X	X		X	X	X	X		X	X	X			
Outpatient visits to CRU						X					X					X	X				X	X
Remind Patients about 7-point SMPG						X					X					X				X		
7-point SMPG							X					X					X				X	
Randomization		X																				
IMP administration ^r		X				X	X up-titra- tion				X	X up-titra- tion				X	X	X				
Medical assessments		Pre	X	X	X	X	X	X	X	X	X	X	X	X	X	X	X	X	X	X	X	
AEs/concomitant medications	X	X	X	X	X	X	X	X	X	X	X	X	X	X	X	X	X	X	X	X	X	
Weight ^t		Pre				Pre	Pre				Pre	Pre				Pre	Pre	Pre			X	X
Body temperature	X	Pre																				X
Vital signs (BP/PR) ^{h,i}	X	Pre, 1, 4, 8, 12	24	48	72	Pre	Pre	24	48	72	Pre	Pre	24	48	72	Pre	Pre	Pre			168	X
12-Lead ECG ^{i,j}		Pre, 8	24	48	72	Pre	Pre				Pre	Pre				Pre	Pre	Pre,	8	24	168	X
PK sampling ^{k,l}		Pre, 8	24	48	72	Pre	Pre				Pre	Pre				Pre	Pre	Pre,	8	24	48	168
Clinical safety lab (hematology, chemistry, urinalysis) ^{m,n}	X		24	48		Pre	Pre	24	48		Pre	Pre	24	48		Pre	Pre	Pre	24	48	168	X
OGTT ^{l,u}	X																			X		
Hemoglobin A1c ^{l,m}		Pre										Pre									168	X
Fasting glucose, insulin, glucagon ^{l,m}		Pre	24			Pre	Pre	24			Pre	Pre	24			Pre	Pre	Pre	24 ^v		168	X
Meal intake and appetite ^w	L/D		L/D																L/D			
Lipid panel ^{l,m,x}		Pre									Pre								24			X

Study Schedule Protocol I8F-JE-GPGC Cohort 1 for Treatment Period

Procedure	Treatment Period (Cohort 1)																				
	-1	1	2	3	4	8	15	16	17	18	22 ±1	29	30	31	32	36 ±1	43 ±1	50	51	52	57

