- [34] have a history or presence of pancreatitis (history of chronic pancreatitis or idiopathic acute pancreatitis) or GI disorder (for example, relevant esophageal reflux or gall bladder disease) or any GI disease that impacts gastric emptying (for example, gastric bypass surgery, pyloric stenosis, with the exception of appendectomy) or could be aggravated by GLP-1 analogues or DPP-IV inhibitors; patients with dyslipidemia and patients who have had cholezystolithiasis (removal of gall stones) and/or cholecystectomy (removal of gall bladder) in the past, with no further sequelae, may be included in the study at the discretion of the investigator
- [35] have a history of atopy or clinically significant multiple or severe drug allergies, intolerance to topical corticosteroids, or severe postdose hypersensitivity reactions (including, but not limited to, erythema multiforme major, linear immunoglobulin A dermatosis, toxic epidermal necrolysis, or exfoliative dermatitis)
- [36] have evidence of significant active neuropsychiatric disease as determined by the investigator
- [37] have a personal or family history of medullary thyroid carcinoma or have multiple endocrine neoplasia syndrome type 2
- [38] have serum AST or ALT $>2\times$ the upper limit of normal (ULN) or total bilirubin (TBL) $>1.5\times$ ULN (with the exception of Gilbert's syndrome)
- [39] have a history of malignancy within 5 years before screening

- [40] have any skin conditions (including, but not limited to, tattoos or scars) that may interfere with the interpretation of assessment or administration of IMP
- [41] are unsuitable for inclusion in the study in the opinion of the investigator or sponsor

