8.1. Discontinuation from Study Treatment

Discontinuation of the IMP for abnormal pancreatic tests **should be considered** by the investigator when a patient meets the following condition:

- lipase and/or amylase are confirmed to be $\geq 3 \times$ ULN. Please refer to algorithm for the monitoring of pancreatic events in [Appendix 6](#).

Discontinuation of the IMP for abnormal liver tests **should be considered** by the investigator when a patient meets 1 of the following conditions after consultation with the Lilly-designated medical monitor:

- ALT or AST $>8 \times$ ULN
- ALT or AST $>5 \times$ ULN sustained for more than 2 weeks
- ALT or AST $>3 \times$ ULN and TBL $>2 \times$ ULN or international normalized ratio >1.5
- ALT or AST $>3 \times$ ULN with the appearance of fatigue, nausea, vomiting, right upper-quadrant pain or tenderness, fever, rash, and/or eosinophilia ($>5\%$)
- alkaline phosphatase (ALP) $>3 \times$ ULN
- ALP $>2.5 \times$ ULN and TBL $>2 \times$ ULN
- ALP $>2.5 \times$ ULN with the appearance of fatigue, nausea, vomiting, right quadrant pain or tenderness, fever, rash, and/or eosinophilia ($>5\%$)

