9.2. Adverse Events

Investigators are responsible for monitoring the safety of patients who have entered this study and for alerting Lilly or its designee to any event that seems unusual, even if this event may be considered an unanticipated benefit to the patient.

The investigator is responsible for the appropriate medical care of patients during the study.

Investigators must document their review of each laboratory safety report.

The investigator remains responsible for following, through an appropriate health care option, AEs that are serious or otherwise medically important, considered related to the IMP or the study, or that caused the patient to discontinue the IMP before completing the study. The patient should be followed up until the event resolves, stabilizes with appropriate diagnostic evaluation, or is reasonably explained. The frequency of follow-up evaluations of the AE is left to the discretion of the investigator.

After the informed consent form is signed, study site personnel will record, via eCRF, the occurrence and nature of each patient's preexisting conditions, including clinically significant signs and symptoms of the disease under treatment in the study. Additionally, site personnel will record any change in the condition(s) and the occurrence and nature of any AEs.

The investigator will interpret and document whether or not an AE has a reasonable possibility of being related to study treatment or a study procedure, taking into account the disease, concomitant treatment, or pathologies.

A "reasonable possibility" means that there is a potential cause and effect relationship between the IMP, study device, and/or study procedure and the AE.

Planned surgeries should not be reported as AEs unless the underlying medical condition has worsened during the course of the study.

If a patient's IMP is discontinued as a result of an AE, study site personnel must report this to Lilly or its designee via eCRF.

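### The prompt liver-test repeat in Protocol 9.4.4.1 is triggered by ALT, ALP or bilirubin but not by AST, although 8.1 considers discontinuation on either aminotransferase

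*Protocol*

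**What the plan says.** Protocol 9.4.4.1 sets the confirmation rule. It begins "If a study patient experiences elevated ALT" (≥3× ULN) and continues with ALP ≥2× ULN or total bilirubin (TBL) ≥2× ULN. On any of these, the liver tests, with a reference to Appendix 5, "should be repeated within 3 to 5 days including ALT, AST, ALP, TBL, direct bilirubin" and others. AST is thus among the tests repeated but not among the values that cause the repeat. If the abnormality persists or worsens, monitoring starts in consultation with the sponsor: "Monitoring should continue until levels normalize and/or are returning to approximate baseline levels". The list in the same section for collecting additional safety data names ALT (≥5× ULN on consecutive tests), TBL and ALP, again without AST. SAP 9.5.7 carries the same trigger and the same list, without the 3-to-5-day interval.

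Elsewhere the protocol treats the two enzymes alike:

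- Exclusion criterion [38] in 6.2 applies to patients who "have serum AST or ALT" above 2× ULN.
- Section 8.1 names ALT or AST in four of its seven liver conditions: above 8×; above 5× for more than 2 weeks; above 3× with TBL above 2× or "international normalized ratio >1.5"; and above 3× "with the appearance of fatigue, nausea, vomiting, right upper-quadrant pain or tenderness, fever, rash, and/or eosinophilia".
- Appendix 4 lists each enzyme above 5-fold as a possible clinically significant event, with confirmation within 48 hours.

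**The concern.** Section 9.4.4.1 is the step that confirms an abnormal value, shows its direction and opens structured monitoring. Section 8.1 is the step that weighs stopping. One would expect any analyte that counts for stopping from 3× ULN to be confirmed from that level too. For ALT it is. For AST alone it is not, and neither document gives a reason.

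A value in this band would be a new rise, because AST above 2× ULN is excluded at entry. What is at stake is prompt confirmation in a few patients. In addition, INR is part of one 8.1 condition but is not on the scheduled panel in Appendix 2. It is reached through the Appendix 5 tests to which the repeat refers. If the repeat is not triggered, nothing directs the site to measure it. No endpoint, sample size or analysis is involved.

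**Working it through.** **Which AST values are left out.** The lower end is 3× ULN, the level used for ALT in 9.4.4.1 and for either enzyme in 8.1. The upper end is 5× ULN, above which Appendix 4 applies, as a guideline. Within that band:

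- TBL ≥2× ULN fires the 9.4.4.1 trigger by itself, and TBL above 1.5-fold is an Appendix 4 item.
- A listed symptom or eosinophilia already meets an 8.1 condition, although 8.1 does not itself ask for a repeat test.
- What remains is AST of about 3× to 5× with ALT below 3×, ALP below 2×, TBL below 2× and no listed symptom or eosinophilia. Of the 8.1 conditions that start at 3×, only the INR part cannot be seen from symptoms or the scheduled panel.

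**Checking the panel schedule.** The days come from the row "Clinical safety lab (hematology, chemistry, urinalysis") in Section 2.

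- Cohort 1: Days 2, 3, 8, 15, 16, 17, 22, 29, 30, 31, 36, 43, 50, 51, 52, 57, 64, 85 (18 panels).
- Cohort 2: Days 2, 3, 8, 15, 16, 17, 22, 29, 36, 43, 44, 45, 50, 51, 52, 57, 64, 85 (18 panels).
- Cohort 3: Days 2, 3, 8, 15, 22, 29, 36, 43, 50, 51, 52, 57, 64, 85 (14 panels).

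Adding screening and Day -1 gives 18 + 2 = 20, 18 + 2 = 20 and 14 + 2 = 16. Appendix 7 states 20 for Cohorts 1 and 2 and 16 for Cohort 3, so the reading agrees. The Cohort 3 row is broken in the text; Day 50 predose is counted because it gives the stated 16.

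**Wait to the next panel, for panels after the first dose and before Day 50 (nominal days).**

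| | 1 day | 5 days | 7 days | Total |
|---|---|---|---|---|
| Cohort 1 | 5 | 3 | 4 (Days 8, 22, 36, 43) | 12 |
| Cohort 2 | 5 | 3 | 4 (Days 8, 22, 29, 36) | 12 |
| Cohort 3 | 1 | 1 | 6 (Days 8, 15, 22, 29, 36, 43) | 8 |

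A panel 1 or 5 days later measures AST again no later than a 3-to-5-day repeat would have to. Only the 7-day gaps exceed the window: 4 of 12, 4 of 12 and 6 of 8. The scheduled value then comes 7 − 5 = 2 to 7 − 3 = 4 days later than a triggered repeat, and on the next dosing day rather than before it.

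The ±1-day visit windows change this little. The 5-day gaps from Day 17 (Cohorts 1 and 2) and Day 31 (Cohort 1) can become 5 + 1 = 6 days. A 7-day gap between two visits that both have windows can reach 7 + 1 + 1 = 9 days.

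**After the last dose.** Days 50 to 51 and 51 to 52 are 1 day each, and Day 52 to 57 is 5 days. Day 57 to 64 is 7 days. Day 64 to 85 is 21 days; with the ±2-day windows, 83 − 66 = 17 to 87 − 62 = 25. These add two gaps over 5 days per cohort, so over all postdose panels the counts are 4 + 2 = 6 of 17, 6 of 17 and 6 + 2 = 8 of 13. No panel is scheduled after Day 85, which is 85 − 50 = 35 days after the last dose, or 35/5 = 7 half-lives at the roughly 5 days given in Protocol 3.2.

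**The case against.** The best defence is that the omission is a consistent choice. The ALT, ALP and TBL set appears in the trigger, in the additional-data list and in the SAP. AST can rise from non-hepatic sources, and a screen for early follow-up need not use the same analytes as a stopping criterion. That may explain a preference, but the protocol does not say so, and it sits awkwardly with 8.1 counting AST from the same 3× level.

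Other parts of the defence stand, and they rule out stronger readings:

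- *AST would be measured again only at the next scheduled panel.* A reader might infer this, but the documents do not support it. Section 9.2 says "Investigators must document their review of each laboratory safety report", Appendix 7 allows extra safety samples, and Appendix 5 allows hepatic tests for a treatment-emergent abnormality. Appendix 1 counts an abnormal laboratory finding as a possible AE, and 9.2 requires follow-up of related or medically important AEs until they resolve, stabilize or are explained, at a frequency the investigator chooses. The next panel is the default, not a limit.
- *Most panels leave a long wait.* Counting every panel whose successor falls on the next dosing day gives 3 + 4 = 7 of 12 in Cohorts 1 and 2 and 1 + 6 = 7 of 8 in Cohort 3. That count includes nominal 5-day gaps, which already lie inside the 3-to-5-day window.
- *A separate INR rule is missing.* The repeat already refers to Appendix 5, which lists INR, and its named tests are not an exhaustive list.

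It is also fair that a repeat confirming the same isolated AST value would still meet no 8.1 condition. It would alter a decision only by finding something new.

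**Conclusion.** The inconsistency is real, and the point holds as a low-priority safety improvement. For an AST of about 3× to 5× ULN with ALT, ALP and TBL below their triggers, neither document requires prompt confirmation or the Appendix 5 work-up. The exposure is small during dosing. The 21-day gap from Day 64 to Day 85 is longer but carries less weight, because no dose remains to be withheld.

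A reader might infer that a stopping rule fails. The documents do not support that: 8.1 is advisory, and an isolated AST rise in this band without symptoms meets none of its conditions.

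The conclusion rests on nominal visit days except where windows are shown, on Appendix 4 being followed above 5-fold, and on the sites following the trigger as written. The local laboratory's turnaround is not stated. The number of patients affected is unknown and probably small.

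**What to change.** In Protocol 9.4.4.1, change the trigger to: *ALT or AST ≥3× ULN, ALP ≥2× ULN, or TBL ≥2× ULN*. Make the same change to the trigger sentence in SAP 9.5.7. For consistency, the additional-safety-data bullet on ALT could read *ALT or AST ≥5× ULN* on consecutive tests. Leave the 8.1 thresholds and Appendix 5 as they are, and add no separate PT/INR rule.

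The cost is one sentence in each document, plus an occasional extra draw for an AST rise that proves non-hepatic. AST is already on every scheduled chemistry panel, and creatine kinase, already among the named repeat tests, helps to interpret such a rise. The change does not justify an amendment of its own and can go into the next one.
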